#### \*exceptions:

- All unsolicited clinical events/laboratory parameters signifying allograft rejection at any time in the study follow-up period and regardless of the need for hospitalization, will be reported as SAEs. Rejection events that are required to be reported to UNOS (United Network for Organ Sharing) will be reported simultaneously to DCP using the Adult Kidney Transplant Recipient Follow-Up Worksheet (https://www.transplantpro.org/wp-content/uploads/sites/3/Adult TRF Kidney.pdf).
- Clinical events or laboratory investigations (e.g., cross-match change) resulting in cancellation of a planned transplant will be reported as SAEs.

#### 11.1.2 AE Data Elements:

The following data elements are required for AE reporting.

- AE verbatim term
- NCI Common Terminology Criteria for Adverse Events version 4.0 (CTCAE v4.0) AE term (MedDRA lowest level term)
- CTCAE (MedDRA) System Organ Class (SOC)
- Event onset date and event ended date
- Treatment assignment code (TAC) at time of AE onset
- Severity grade
- Attribution to study agent (relatedness)
- Whether or not the event was reported as a SAE
- Whether or not the participant dropped due to the event
- Outcome of the event

#### 11.1.3 Severity of AEs

11.1.3.1 Identify the AE using the CTCAE version 4.0. The CTCAE provides descriptive terminology (MedDRA lowest level term) and a grading scale for each AE listed. A copy of the CTCAE can be found at http://ctep.cancer.gov/protocolDevelopment/electronic applications/ctc.htm [37].

AEs will be assessed according to the grade associated with the CTCAE term. AEs that do not have a corresponding CTCAE term will be assessed according to the general guidelines for grading used in the CTCAE v4.0. as stated below.

#### CTCAE v4.0 general severity guidelines:

Grade	Severity	Description				
1	Mild	Mild; asymptomatic or mild symptoms; clinical or diagnostic				
		observations only; intervention not indicated.				
2	Moderate	Moderate; minimal, local or noninvasive intervention indicated;				
		limiting age-appropriate instrumental activities of daily living				
		(ADL)*.				

- 1			1100001 (61510115.11)
	3	Severe	Severe or medically significant but not immediately life-threatening;
			hospitalization or prolongation of hospitalization indicated;
			disabling; limiting self-care ADL**.
ĺ	4	Life-threatening	Life-threatening consequences; urgent intervention indicated.
	5	Fatal	Death related to AE.

#### ADL

- \*Instrumental ADL refers to preparing meals, shopping for groceries or clothes, using the telephone, managing money, *etc*.
- \*\*Self-care ADL refers to bathing, dressing and undressing, feeding self, using the toilet, taking medications, and not bedridden.

#### 11.1.4 Assessment of relationship of AE to treatment

The possibility that the AE is related to study agent will be classified as one of the following: not related, unlikely, possible, probable, or definite.

# 11.1.5 Follow-up of AEs

All AEs, including lab abnormalities that in the opinion of the investigator are clinically significant, will be followed according to good medical practices and documented as such.

#### 11.2 Serious Adverse Events

- 11.2.1 DEFINITION: Regulations at 21 CFR §312.32 (revised April 1, 2014) defines an SAE as any untoward medical occurrence that at any dose has one or more of the following outcomes:
  - Death
  - A life-threatening AE
  - Inpatient hospitalization or prolongation of existing hospitalization
  - A persistent or significant incapacity or substantial disruption of the ability to perform normallife functions
  - A congenital anomaly or birth defect
  - Important medical events that may not be immediately life-threatening or result in death or hospitalization should also be considered serious when, based upon appropriate medical judgment, they may jeopardize the patient and may require intervention to prevent one of the other outcomes.

All unsolicited clinical events/laboratory parameters signifying allograft rejection at any time in the study follow-up period and regardless of the need for hospitalization, will be reported as SAEs. Rejection events that are required to be reported to UNOS (United Network for Organ Sharing) will be reported simultaneously to DCP using the Adult Kidney Transplant Recipient Follow-Up Worksheet (https://www.transplantpro.org/wp-content/uploads/sites/3/Adult TRF Kidney.pdf).

Clinical events or laboratory investigations (e.g., cross-match change) resulting in cancellation of a planned transplant will be reported as SAEs.

### 11.2.2 Reporting SAEs to DCP

a. All SAEs, including all hospitalizations, during the study period will be reported as per DCP SAE reporting procedures, with the following exception.

- i. Hospitalization for planned renal transplant surgery will not be reported. However, if this hospitalization event lasts longer than the usual period at the institution (as determined by the Site Principal Investigator or Sponsor), it will be reportable as an SAE. Adverse events (AEs) relevant to the prolongation of this hospitalization will also be collected and reported on AE CRFs.
- b. In situations prompting SAE reporting when multiple abnormalities/associated concurrent/concomitant adverse events are present:
  - i. The primary/most significant adverse event will be recorded as the SAE. Associated events should be included in the chronology of the case provided in the 'Describe Event' field on the SAE form. Multiple signs and symptoms can be incorporated under a single diagnosis, disease, or condition. These associated events should not be separately reported as AEs on AE CRFs.

Example: pneumonia resulting in hospitalization would be the primary SAE, and concomitant events such as leukocytosis, anemia, fever, etc. can be reported in the 'Describe Event' field on the SAE form but would not be listed separately as AEs on AE CRFs.

ii. Concurrent/concomitant events that prolong hospitalization, or that independently fulfill other serious adverse event reporting criteria (e.g., life-threatening, medically significant), will be reported as separate SAEs.

Example: pneumonia resulting in hospitalization, along with renal failure requiring dialysis, will be reported separately as two SAEs as (i) pneumonia, and (ii) renal failure requiring dialysis.

- 11.2.2.1 The Lead Organization and all Participating Organizations will report SAEs on the DCP SAE Report Form found at http://prevention.cancer.gov/clinical-trials/clinical-trials-management/protocol-information-office/pio-instructions-and-tools/2012-consortia.
- 11.2.2.2 Contact the DCP Medical Monitor by phone within 24 hours of knowledge of the event.

[name]

Chief, Lung & Upper Aerodigestive Cancer Research Group

Division of Cancer Prevention

National Cancer Institute

[name]

[name] (For FedEx, use [name])

[contact] [contact]

Email: [contact]

Include the following information when calling the Medical Monitor:

- Date and time of the SAE
- Date and time of the SAE report
- Name of reporter
- Call back phone number
- Affiliation/Institution conducting the study
- DCP protocol number
- Title of protocol
- Description of the SAE, including attribution to drug
- 11.2.2.3 The Lead Organization and all Participating Organizations will email written SAE reports to the following within 48 hours of learning of the event using the fillable PDF SAE Report Form.

- DCP's Regulatory Contractor CCS Associates, Inc. (CCSA; [contact]) at [contact]
- NCI DCP Medical Monitor, [name] ([contact])
- Northwestern Cancer Prevention Consortium ([contact])
- 11.2.2.4 The DCP Medical Monitor and CCSA regulatory and safety staff will determine which SAEs require FDA submission as IND safety reports.
- 11.2.2.5 The Lead Organization and all Participating Organizations will comply with applicable regulatory requirements related to reporting SAEs to the CIRB/IEC.

# 11.2.3 Follow-up of SAE

Site staff should send follow-up reports as requested when additional information is available. Additional information should be entered on the DCP SAE Report Form in the appropriate format. Follow-up information should be sent to DCP as soon as available. All SAEs will be followed according to standard of care. SAEs possibly, probably, or definitely related to the study agent will be followed until resolved. Serious AEs (SAEs) will be monitored throughout the study regardless of cause by the study physicians and the Data and Safety Monitoring Board (DSMB).

#### 12. STUDY MONITORING

### 12.1 Data Management

Data will be managed by the study statistician, [name], according to standard operating procedures, which meet the guidelines of DCP Requirements for Data Management and which follow the Data Management Plan that Northwestern University has on file with the Division of Cancer Prevention, NCI. Source data verification will be performed by the Northwestern Cancer Prevention Consortium. The Consortia 2012 Data Management Plan, submitted as part of a contract agreement with the NCI (HHSN261201200035I), was approved.

Clinical data will be reported to the Lurie Cancer Center Clinical Trials Management System (CTMS), which will be the database of record.

# 12.2 Case Report Forms

Participant data will be collected using protocol-specific case report forms (CRFs) developed from the standard set of DCP Chemoprevention CRF Templates and utilizing NCI-approved Common Data Elements (CDEs). The approved CRFs will be used by Northwestern University to create the electronic CRFs (e-CRFs) screens in the CTMS-RDC application. Site staff will enter data into the e-CRFs for transmission to DCP according to DCP standards and procedures.

All specimen results that are batch analyzed will be collected and stored on excel spreadsheets. The excel spreadsheets will constitute the database of record.

#### 12.3 Source Documents

All source documents will be collected and stored by the research staff at the site of accrual. Any data recorded directly in CTMS that constitute no prior written or electronic record of data, will be specifically identified as source data. Questionnaires completed in person may be completed on paper and entered into CTMS.

#### 12.4 Data and Safety Monitoring Plan

A comprehensive Data Safety and Monitoring Plan has been submitted by Northwestern University, approved by the DCP, and is on file there. Any future changes will be forwarded for review.

This trial is subject to review by the Lurie Cancer Center Data & Safety Monitoring Committee (DSMC). Semi-Annual reports, SAEs, and protocol deviations will be reviewed by the DSMC at bi-weekly meetings. This trial is also subject to possible audits by the Lurie Cancer Center Clinical Trials Audit Committee (CTAC).

#### 12.5 Sponsor or FDA Monitoring

The NCI, DCP (or their designee), pharmaceutical collaborator (or their designee), or FDA may monitor/audit various aspects of the study. These monitors will be given access to facilities, databases, supplies, and records to review and verify data pertinent to the study.

#### 12.6 Record Retention

Clinical records for all participants, including CRFs, all source documentation (containing evidence to study eligibility, history and physical findings, laboratory data, results of consultations, *etc.*), as well as CIRB records and other regulatory documentation will be retained by the Investigator in a secure storage facility in compliance with Health Insurance Portability and Accountability Act (HIPAA), Office of Human Research Protections (OHRP), Food and Drug Administration (FDA) regulations and guidances, and NCI/DCP requirements, unless the standard at the site is more stringent. The records for all studies performed under an IND will be maintained, at a minimum, for two years after the approval of a New Drug Application (NDA). For NCI/DCP, records will be retained for at least three years after the completion of the research. NCI will be notified prior to the planned destruction of any materials. The records should be accessible for inspection and copying by authorized persons of the Food and Drug Administration. If the study is done outside of the United States, applicable regulatory requirements for the specific country participating in the study also apply.

# 12.7 Cooperative Research and Development Agreement (CRADA)/Clinical Trials Agreement (CTA)

Not applicable.

#### 13. STATISTICAL CONSIDERATIONS

#### 13.1 Study Design/Description

This is a prospective single-arm trial to evaluate if the Gardasil® 9 HPV vaccine induces and sustains an adequate immune response at 12-months post-transplantation among 18-49 year old kidney transplant recipients when ≥ 1 doses of the vaccine are administered prior to transplantation. The study population includes candidates for renal transplant within 12 months of enrollment at five transplant centers in the United States. We anticipate that 96 eligible kidney transplant recipients will ultimately be enrolled and complete follow-up during the study period of 36 months, and 24-28 of them will have received the second vaccine dose before their transplant. For the analytical dataset for the primary endpoint, participants will have received the first dose of Gardasil® 9 nonavalent HPV vaccine at baseline and their post-transplant serology titers are assessed at 12-months post-transplant visit. Kidney transplant candidates who receive one or two doses of the vaccine but do not get transplanted within 12 months of enrollment will be considered off-study after they are offered the remainder of the vaccine doses to complete the three-dose vaccine series.

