#### **Feasibility**

According to the 2017 Organ Procurement Transplantation Network data reports [22], a total of 467 first-time kidney transplants in adults aged 18-49 were performed at these five sites (Table 1). First-time renal transplant recipients in adults aged 18-49 at these institutions included 34.7% white, 26.5% African American, 25.9% Hispanic, 11.8% Asian, 0.6% Pacific Islander, and 0.6% Multiracial – a larger percentage of non-white living donor transplant recipients (65%) than the national average (34%). Recruitment of pre-renal transplant recipients will occur over a period of 18 months. Investigators will review all listed individuals undergoing evaluation for transplantation on a weekly basis.

We project that 815 adults, ages 18-49 years, will receive a first-time kidney transplant during an 18-month period based on the 543 adult first-time kidney transplant recipients aged 18-49 in 2017 by the participating transplant centers (Table 1), suggesting that our recruitment goal is highly feasible. The final analytic sample for follow-up will include an estimated 64 adults (which are projected to include 23 white, 17 African-American, 17 Hispanic, 7 Asian based on current racial/ethnic composition of kidney transplant recipients) who have received two doses of the Gardasil® 9 HPV vaccine and have undergone a kidney transplant  $\geq$  30 days after the first vaccine dose. To meet this goal, we estimate that we need to recruit and consent 180 participants.

Table 1. Numbers of Kidney Transplants in 2017 by Center									
	CSMC	UCSF	NW	UAB	UNC	Total			
First-time living donor kidney transplants in women age 18-49, 2017*	10	18	16	19	4	67			
First-time living donor kidney transplants in men age 18-49, 2017*	10	28	40	31	4	113			
First-time deceased donor kidney transplants in women age 18-49 years, 2017*	19	30	30	31	16	126			
First-time deceased donor kidney transplants in men age 18-49 years, 2017*	32	40	21	54	14	161			
Total first-time kidney transplants in women and men age 18-49, 2017	71	116	107	135	38	467			
*https://optn.transplant.hrsa.gov/data/view-data-reports/center-data accessed on 11/06/2018.									

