Time for kidney transplants will vary significantly between those receiving a living donor transplant and those receiving a deceased donor transplant. Typically, living donor kidney transplants are performed within 90 days after approval of an acceptable living donor at each of the participating transplant centers. We will make every effort to complete the screening evaluations and schedule the baseline visit ≥30 days before the patient's living donor kidney transplant procedure to maximize the number of eligible, consented participants who receive at least one dose of the Gardasil® 9 HPV vaccine prior to the transplant. Study participants who are expected to receive a kidney transplant from a deceased donor will be selected based on their likelihood of receiving the transplant within 12 months of enrollment, and depending on when the transplant actually gets scheduled (unpredictable time frame, given the knowledge of availability of a donor kidney and transplant surgery is usually a matter of <24 hours), the participants may be able to receive one, two or all three doses of the HPV vaccine prior to transplant.

Over an 18-month period we expect that 180 kidney transplant candidates will be consented and pass the medical chart review and pre-transplant clinic evaluations; 120 will receive one or two doses of the Gardasil® 9 HPV vaccine prior to transplant; 96 women will complete the 12-month post-transplant follow-up visit and receive the booster vaccine dose; and 64 women who have received the first vaccine dose > 30 days before their transplant will complete all follow-up.

Although all eligible, consented kidney transplant candidates will receive their first vaccine dose, we expect that a substantial fraction (perhaps one-third) of these candidates may not receive a transplant within the study period, largely because the identified donor will not pass through all the transplant eligibility screening testing in case of living donor transplant recipients, or no matching kidney from deceased donors becomes available in case of participants on the deceased donor transplant waiting list. Therefore, to meet the sample size requirement (N=64) for analysis of our primary endpoint, we enroll a higher number of participants than our expected target, expecting losses to follow-up at several stages in the study enrollment and follow-up cascade.

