# 13.3 Accrual and Feasibility

Sample size: Consent/enrollment = 180; Intervention = 96; Analytic sample = 64 after drop-outs. The expected accrual rate is 10 participants per month across five sites, and the planned recruitment duration is 18 months. We anticipate that all evaluable participants will have completed all study procedures within 36 months.

Initial accrual estimates were calculated based on; 1) the number of kidney transplant candidates aged 18-49 who come forward for kidney transplant who eventually get transplanted; and 2) the number of kidney transplants performed in this age sub-set at the five participating transplant centers in 2017.

After accounting for experiences in recruitment of participants during the years the protocol has been open, as well as the additional accrual and retention challenges encountered due to the COVID-19 pandemic, it was projected that the expected accrual for the study will be in the range of n=24 to 28 participants who will receive one or more vaccine doses pre-transplant and complete the necessary post-transplant follow-up period for the primary endpoint analysis.

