# 13.4 Primary Objective, Endpoint(s), Analysis Plan

The primary objective is to estimate HPV vaccine-type-specific seroconversion rates at 12-months post-transplantation among kidney transplant recipients who receive  $\geq 1$  doses of the Gardasil® 9 HPV vaccine prior to transplantation,

An estimate of the seroconversion rate will be provided along with exact Clopper-Pearson 95% confidence intervals (CIs).

Originally (until version 3.10), the study was designed with the expectation of at least n=64 evaluable participants for the primary analysis, and the analytic plan was focused on comparisons with prespecified benchmarks (e.g., 0.75 and 0.90) of the expected seroconversion rate estimate.

In version 3.11, responding to the lower accrual expectations of between n=24 to n=28 evaluable participants in the study, the study's focus was revised to only focus on description of the estimation of the seroconversion rate and the upper limit of its one sided 95% confidence interval, as opposed to any pre-specified comparisons.

Even without pre-specified comparison benchmarks, the revised analysis plan will permit cross-study comparisons with other relevant HPV vaccination studies (e.g., those conducted among individuals undergoing solid organ transplants or other immunosuppressed individuals). The study will generate key preliminary data for testing clinically relevant hypotheses in future larger studies to evaluate the full extent of protection afforded by HPV vaccination administered prior to transplant.

With the study expecting to yield between n=24 to n=28 evaluable participants, Table 3 (below) provides expected upper limits of the one sided 95% CI for the estimates of the seroconversion rates ranging between 0.65 to 0.90.

Table 3. Expected upper limits of one sided 95% CI for seroconversion rates				
Expected accrual n=24 evaluable	Expected accrual n=28 evaluable			
participants	participants			

	One-sided 95%CI		One-sided 95%CI
Estimate P	Upper Limit	Estimate P	Upper Limit
0.65	0.8088	0.65	0.7977
0.70	0.8480	0.70	0.8380
0.75	0.8851	0.75	0.8763
0.80	0.9197	0.80	0.9123
0.90	0.9776	0.90	0.9739

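### Section 13.1 presents 24-28 as a two-dose subset of 96 completers, while 13.3, 13.4, Table 3 and 13.6 make 24-28 the whole evaluable sample

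*Combined protocol and SAP*

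**What the plan says.** The documents give these counts, all in current text:

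- **13.1:** the number of completers comes first: "We anticipate that 96 eligible kidney transplant recipients will ultimately be enrolled and complete follow-up during the study period of 36 months". The same sentence then singles out a subset of these completers by dose history: "24-28 of them will have received the second vaccine dose before their transplant".
- **13.3, first line:** "Sample size: Consent/enrollment = 180; Intervention = 96; Analytic sample = 64 after drop-outs". Two paragraphs later comes a projection revised for recruitment experience and the pandemic: "expected accrual for the study will be in the range of n=24 to 28 participants who will receive one or more vaccine doses pre-transplant". These participants must also finish follow-up for the primary analysis.
- **13.4:** "Originally (until version 3.10), the study was designed with the expectation of at least n=64 evaluable participants for the primary analysis". For version 3.11: "With the study expecting to yield between n=24 to n=28 evaluable participants, Table 3 (below) provides expected upper limits". Those limits belong to a one-sided 95% interval.
- **13.6:** a 20% drop-out is said to leave 24-28 completers. No starting number is given.
- **4.4, Feasibility:** "The final analytic sample for follow-up will include an estimated 64 adults", described as having had two doses. The section sets out a cascade of 180 consented, 120 vaccinated before transplant, 96 at the 12-month visit and 64 completing all follow-up, and enrolment is set "to meet the sample size requirement (N=64) for analysis of our primary endpoint".

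On who counts, 1.1 and 8.1 define the primary set as recipients with at least one dose given 30 days or more before transplant. Sections 13.1 and 13.4 restate the set without the 30-day condition.

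**The concern.** The pair 24-28 carries two incompatible meanings. In 13.1 it is the part of 96 completers who had a second dose before surgery. In 13.3, 13.4 and 13.6 it is everyone who can be analysed, whether they had one, two or three pre-transplant doses. Section 13.1 opens the statistical chapter, so a reader who starts there expects 96 completers and a two-dose stratum of 24-28. The version 3.11 design yields 24-28 people in total, to be divided over the three dose strata of the secondary analysis in 13.5.

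The remaining statements of 64 as the current sample and requirement add a third size. The 20% in 13.6 cannot be traced to any stated number. At stake is the precision a reader would expect of the primary estimate.

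**Working it through.** **1. Which n does Table 3 use?** Inputs are the printed rates P and n=24 or 28. The exact (Clopper-Pearson) one-sided 95% upper limit is the 0.95 quantile of a Beta(nP+1, n−nP) distribution, with fractional nP allowed.

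| P | n=24 printed | n=24 computed | n=28 printed | n=28 computed |
|---|---|---|---|---|
| 0.65 | 0.8088 | 0.8087 | 0.7977 | 0.7977 |
| 0.70 | 0.8480 | 0.8480 | 0.8380 | 0.8380 |
| 0.75 | 0.8851 | 0.8851 | 0.8763 | 0.8763 |
| 0.80 | 0.9197 | 0.9197 | 0.9123 | 0.9123 |
| 0.90 | 0.9776 | 0.9776 | 0.9739 | 0.9739 |

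All ten agree to within 0.0001. Table 3 is right, and it takes 24-28 as the full evaluable n.

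**2. Can 13.1 be squared with that?** If 24-28 are a subset of 96, they are 24/96 = 25% to 28/96 = 29% of completers, and the other 68-72 completers with a first dose and a 12-month sample would also belong to the primary set. Sections 13.3, 13.4 and 13.6 leave no room for them.

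**3. Does a 20% drop-out give 24-28?** Remaining = base × 0.80; loss needed = 1 − 28/base to 1 − 24/base.

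| Base | Source | After 20% loss | Loss needed to reach 24-28 |
|---|---|---|---|
| 180 | 4.4, 13.3 | 144 | 84-87% |
| 120 | 4.4 | 96 | 77-80% |
| 96 | 4.4, 13.1, 13.3 | 76.8 | 71-75% |
| 64 | 4.4, 13.3 | 51.2 | 56-63% |

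In reverse, 24/0.80 = 30 and 28/0.80 = 35. No 30-35 appears in the documents. The only stated step equal to 20% is 120 to 96 in the older cascade.

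**4. Effect on precision.** The rate of 0.80 is assumed here; it is one of the Table 3 rows. Two-sided exact 95% limits are the 0.025 quantile of Beta(nP, n−nP+1) and the 0.975 quantile of Beta(nP+1, n−nP).

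| n | Two-sided 95% interval | Width | One-sided 95% upper limit |
|---|---|---|---|
| 96 | 0.706-0.875 | 0.17 | 0.865 |
| 64 | 0.681-0.890 | 0.21 | 0.878 |
| 28 | 0.607-0.926 | 0.32 | 0.912 |
| 24 | 0.588-0.934 | 0.35 | 0.920 |

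Whole-number counts give the same picture: 77/96 gives 0.708-0.876 (width 0.17) and 19/24 gives 0.578-0.929 (width 0.35). The width ratio is 0.35/0.17, about 2, for n=24 against n=96, and 0.35/0.21, about 1.7, against n=64.

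**5. A side check in 4.4.** Table 1 totals 71+116+107+135+38 = 467 by centre and 67+113+126+161 = 467 by row, and the text above it also says 467. The 18-month projection uses 543 instead: 543 × 1.5 = 814.5, printed as 815. From 467 it would be 467 × 1.5 = 700.5.

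**The case against.** The best case for the plan is that a full reading resolves most of this. Section 13.4 dates the 64 to the period before version 3.11, the second paragraph of 13.3 speaks of initial estimates, and the third gives the revised 24-28. Table 3 prints the planned precision at the right n, so nobody has to derive it from 13.1. No version gave 96 as the primary analysis n, so 64 is arguably the fairer comparator. Version 3.11 has no benchmark test, so no decision rule hangs on the sentence. The drop-out table tests bases that largely belong to the older design. The 30-day rule also appears in the dosing section and Appendix B.

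Several of these points stand. A careful reader can infer that 64 is superseded, although 4.4 has no nearby cue. The 20% is better called a missing base than a failed calculation. The 30-day wording and the 543 are secondary. That 180, 120 and 96 were superseded along with 64 is my reading of 13.3 and 13.4, since 13.4 withdraws only the 64 by name.

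None of this rescues 13.1. That sentence already carries the revised 24-28 and attaches it to the wrong population. Read literally, with 96 completers who had a first dose and a 12-month titre, it makes 96 the primary n, so 96 is a fair comparator alongside 64.

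**Conclusion.** The concern holds. Section 13.1 is wrong as written: 24-28 is the expected total for the primary analysis, not a two-dose subset of 96. The present-tense 64 in 4.4 and in the first line of 13.3 compounds the error. A reader relying on 13.1 would expect an interval about half as wide as n=24 can give; one relying on 4.4 would expect about 0.21 instead of 0.32-0.35. These widths assume a rate of 0.80 and exact intervals.

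This is an inconsistency in stated counts, not a computing error. Table 3, the estimator and the conduct of the trial are unaffected. It should be fixed, chiefly for 13.1 and the remaining 64s. The drop-out base, the 30-day wording and the 543 against 467 mismatch are tidying.

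**What to change.** - **13.1:** replace the 96 completers and the second-dose subset with 24-28 evaluable participants in total, each with one or more pre-transplant doses.
- **13.3 (first line) and 4.4:** label the 180/120/96/64 projections (180/96/64 in 13.3) as original, through version 3.10, and point to 24-28 as the current expectation. The sponsor should confirm whether any of the earlier-stage figures is still in force.
- **13.6:** state the number to which the 20% applies, or restate the rate. The 30-35 above is a back-calculation for the sponsor to confirm.
- **13.1 and 13.4:** use the primary set of 1.1 and 8.1, including the 30-day condition, and specify a 12-month sample. Section 13.8, which covers everyone with at least one dose, can stay broader if it says it is not the primary analysis set.
- **4.4:** bring 543 and 815 into line with Table 1 (467, and about 700 over 18 months), or explain the source of 543.

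The cost is protocol wording only: no extra participants and no change to Table 3 or the estimator. The one downside is that the stated size becomes less favourable.
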